5.2.9 Conditions for Withdrawal

Subjects and/or subject's parent/LAR will be informed that they have the right to withdraw and/or withdraw their child from the study at any time.

- At the discretion of the Investigator or Sponsor due to safety concerns or significant non-compliance with the protocol (based on the Investigator's judgment), without the subject's permission (withdrawal)
- At the request of the subject (dropout)

The following will result in automatic withdrawal or exclusion of a subject from the study:

- Significant non-compliance with the protocol, based on the Investigator's judgment

The reason for a withdrawal or dropout should be clearly documented in the source documents and in the CRB.

The Investigator must determine whether voluntary withdrawal is due to safety concerns (in which case, the reason for discontinuation will be noted as "AEs") or for another reason.

Withdrawn subjects may be replaced.

Subjects included in the Immunogenicity Persistence and Booster Phase Cohort 2 (adult subset) will not be withdrawn from the study if they fail to come to one or more visits prior to booster dose (at M6, M12, and/or M18).

5.2.10 Lost to Follow-up Procedures

In the case of subjects who fail to return for a follow-up examination, documented reasonable effort (ie, documented telephone calls and certified mail) should be undertaken to locate or recall them, or at least to determine their health status while fully respecting their rights. These efforts should be documented in the source documents.

5.2.11 Classification of Subjects Who Discontinue the Study

For any subject who discontinues the study prior to completion, the most significant reason for early termination will be checked in the CRB. Reasons are listed below from the most significant to the least significant (refer to the CRF completion instructions for additional details and examples):

Adverse Event	To be used when the subject is permanently terminated from the study because of an AE (including an SAE), as defined in Section 9.2.1.1 . This category also applies if the subject experiences a definitive contraindication that is an SAE or AE.
Lost to Follow-up	To be used when the subject cannot be found or contacted in spite of efforts to locate him/her before the date of his/her planned last visit, as outlined in Section 5.2.10 . The certified letter was sent by the Investigator and returned unsigned, and the subject or parent/guardian did not give any other news and did not come to any following visit.
Protocol Deviation	To be used: 
• In case of significant non-compliance with the protocol (eg, deviation of the Inclusion / Exclusion criteria, non-compliance with time windows, administration of other vaccine, blood sampling or vaccination refusal, missed injection/treatment, or error in the vaccine/treatment administration)• If the subject experiences a definitive contraindication that is not an SAE or AE• The subject or the parent/guardian signed the certified letter sent by the Investigator but did not give any other news and did not come to any following visit
Withdrawal by Subject or Parent / Guardian / Legally Acceptable Representative	To be used: 
• When the subject or parent/guardian indicated unwillingness to continue in the study• When the subject or parent/guardian made the decision to discontinue participation in the study for any personal reason other than an SAE/AE (eg, subject is relocating, informed consent withdrawal, etc.)

5.2.12 Follow-up of Discontinuations

The site should complete all scheduled safety follow-ups and contact any subject who has prematurely terminated the study because of an AE or a protocol deviation.

For subjects where the reason for early termination was lost to follow-up or if the subject withdrew informed consent and specified that they do not want to be contacted again and it is documented in the source document, the site will not attempt to obtain further safety information.

If the subject's status at the end of the study is "Withdrawal by Subject or Parent / Guardian / LAR", the site will attempt to contact them for the 6-month follow-up except if they specified that they do not want to be contacted again and it is documented in the source document.

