Phase III Study, 5 Visits, 1 Phone Call, 3 Vaccinations, 3 Blood Samples, 7 Months Period per Subject

Visit	V01	V02	V03	V04	V05	Phone Call
Visit interval	VAC1	VAC2= VAC1+7D	VAC3 = VAC1+28D	VAC3+14D	VAC3+28D	VAC3*+6M
Indicative days (D)	D0	D7 +1D	D28 ±3D	D42 ±3D	D56 ±3D	M7 +14D
Informed consent signed†	√					
Demographic data	√					
Urine pregnancy test‡	√	√	√			
Physical examination§	√	√	√	√	√	
Past and current significant medical history	√					
Inclusion & exclusion criteria	√					
Randomization/ IRT call	√	√	√			
Blood sampling for serology**	BL01		BL02	BL03		
Vaccine injection	√	√	√			
30-minute observation period	√	√	√			
Diary Card (DC) Memory Aid (MA)						
Provided	DC1	DC2	DC3		MA1	
Checked		DC1	DC2	DC3	DC3	MA1
Collected		DC1	DC2		DC3	
Injection site reactions and Systemic Event Assessment	√	√	√	√	√	
Temporary contraindications		√	√			
Definitive contraindications		√	√			
Reportable concomitant medication	√	√	√	√	√	
Termination Record					√	
Pregnancy cases	Collected throughout the entire study period					
SAEs and AESIs	Collected throughout the entire study period					

* VAC3 or last vaccine injection in the event of early terminated subject contacted for the 6 months follow-up period through a phone call

† In addition if applicable, one AF has to be signed by subjects as required by local Ethics Committee or country regulations

‡ For subjects of childbearing potential

§ Complete physical examination at V01 and medically-driven physical examination for remaining visits

** Blood sample volume drawn from subjects aged 1 year to < 2 years will be 3 mL for subjects ≥ 2 years to < 18 years will be 5 mL, and for subjects ≥ 18 years will be 6 mL

One Week 2-Dose Primary Series – Adults (Cohort 2)

Phase III Study, 4 Visits, 1 Phone Call, 2 Vaccinations, 2 Blood Samples, approximately 7 Months Period per Subject

Visit	V01	V02	V03	V04	Phone Call‡
Visit interval	VAC1	VAC2= VAC1+7D	VAC1+28D	VAC2+28D	VAC2*+6M
Indicative days (D)	D0	D7 +1D	D28 ±3D	D35 ±3D	M6 +14D
Informed consent signed	√				
Demographic data	√				
Urine pregnancy test‡	√	√			
Physical examination§	√	√	√	√	
Past and current significant medical history	√				
Inclusion & exclusion criteria	√				
Randomization/ IRT call	√	√			
Blood sampling for serology**	BL01		BL02		
Vaccine injection	√	√			
30-minute observation period	√	√			
Diary Card (DC) Memory Aid (MA)					
Provided	DC1	DC2		MA	
Checked		DC1	DC2	DC2	
Collected		DC1		DC2	MA

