Safety will be assessed in all subjects during the vaccination period and up to 28 days after vaccinations, in terms of occurrence of AEs, SAEs and Adverse Events of Special Interest (AESIs). In addition, SAEs and AESIs will be collected up to 6 months after the last vaccination in all subjects. The duration of the safety follow-up is planned to be until 6 months after the last dose of vaccine in the primary series and up to approximately 18 or approximately 30 to 42 months for the subsets of adult subjects who will receive the single booster dose (Cohorts 1 and 2, respectively). For adult subjects in Immunogenicity Persistence and Booster Phase Cohort 2, between the 6-month follow-up visit after primary series (V05) and booster dose visit (V08), AESIs will not be collected, only fatal SAEs and related SAEs will be collected.

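### Protocol 5.2.12 drops the 6-month safety call for subjects classed as lost to follow-up, which does not agree with 6-month SAE/AESI collection in all subjects; the effect is probably small and the repair is cheap

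*Protocol*

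**What the plan says.** Protocol Section 5.2.12 sets the follow-up by reason for discontinuation.

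- Subjects terminated for an adverse event or a protocol deviation are contacted, and their scheduled safety follow-up is completed.
- For voluntary withdrawals, "the site will attempt to contact them for the 6-month follow-up", unless a documented refusal of contact exists.
- The third rule begins "For subjects where the reason for early termination was lost to follow-up or if the subject withdrew informed consent". For withdrawn consent it adds the condition of a documented wish not to be contacted. Its instruction for both kinds of subject is that "the site will not attempt to obtain further safety information".

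Section 5.2.11 reserves the lost class for a subject who "cannot be found or contacted in spite of efforts to locate him/her before the date of his/her planned last visit". It adds that "The certified letter was sent by the Investigator and returned unsigned", with no other news and no later visit. Section 5.2.10 sets the effort that comes first: "documented reasonable effort (ie, documented telephone calls and certified mail) should be undertaken to locate or recall them", or at least to learn their state of health.

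Two other places speak to the same 6-month contact. Section 5.1.1 states that "SAEs and AESIs will be collected up to 6 months after the last vaccination in all subjects". In the Tables of Study Procedures for the two primary series, the footnote to the 6-month call gives as reference dose the third (Cohort 1) or second (Cohort 2) vaccination, or "last vaccine injection in the event of early terminated subject contacted for the 6 months follow-up period through a phone call". The SAP repeats that footnote in Tables 3.2 to 3.4.

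**The concern.** A lost subject has not refused contact, yet is placed under the same rule as someone who has. The 6-month call is a separate, later contact by telephone. Failing to find someone around the last clinic visit does not show that they cannot be reached months afterwards. If the call is not attempted, any SAE or AESI in the intervening months reaches the database only if the subject or a third party reports it.

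At stake is the completeness of the 6-month SAE/AESI record for VRVg-2. Section 1.3.2 puts earlier exposure to the selected dose at 80 adults. Sites also need one consistent instruction on whether to make the call.

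**Working it through.** The plan states no figure for this rule, so there is none to reproduce. The check compares the texts and then gives an illustration on assumed rates.

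**Do the rules cover the same subject?** Section 5.2.11 lists lost to follow-up among the reasons for early termination. A lost subject is therefore an early-terminated subject under the footnote and one of all subjects under 5.1.1. Only 5.2.12 removes that subject from the call.

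**How long is the gap?** Section 5.2.11 ties the class to the planned last visit. The Synopsis describes the last contact as a phone call, not a visit, so the two are distinct. In primary-series-only subjects the last visit is V05 (D56) in Cohort 1 and V04 (D35) in Cohort 2. Each falls 28 days after the last dose, and the termination record is completed there. The call is due 6 months after the last dose. The gap is 6 months minus 28 days, about 5 months.

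**Who is affected?** Only subjects for whom calls failed and the letter came back unsigned. Under 5.2.11, someone who signs for the letter but gives no news and stops attending is a protocol deviation, and 5.2.12 has the site contact that person.

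**How are they counted?** SAP Section 5.1.2.2 treats SAEs and AESIs as unsolicited events, with all vaccinated subjects as denominator. A lost subject counts as event-free for the months not collected. The same section gives documented safety as the general basis for denominators, to avoid understating incidence.

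**Illustration.** Inputs: 1700 planned subjects, of whom 303 + 303 + 414 = 1020 are on VRVg-2 (SAP Table 3.1). The loss rate d is assumed to be 1% to 10%. The 15% attrition in the sample size section is non-evaluability for the per-protocol set and cannot stand in for it. With n = 1020 × (1 − d):

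- Exact one-sided 95% upper bound with zero events: 1 − 0.05^(1/n).
- Chance of at least one event at a true rate of 0.1%: 1 − 0.999^n.
- Reading of a true 2.00% rate: 2.00% × (1 − d), assuming equal risk and none of a lost subject's events captured.

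| d | Lost of 1700 | Lost of 1020 | Upper bound | Chance of ≥ 1 event | 2.00% reads as |
|---|---|---|---|---|---|
| 0 | 0 | 0 | 0.293% | 0.640 | 2.00% |
| 1% | 17 | 10 | 0.296% | 0.636 | 1.98% |
| 2% | 34 | 20 | 0.299% | 0.632 | 1.96% |
| 5% | 85 | 51 | 0.309% | 0.621 | 1.90% |
| 10% | 170 | 102 | 0.326% | 0.601 | 1.80% |

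If lost subjects had twice the risk, the relative understatement would be 1 − (1 − d)/((1 − d) + 2d). That is 1 − 0.98/1.02 = 3.9% at d = 2% and 1 − 0.95/1.05 = 9.5% at d = 5%. For a given d and risk ratio these figures are ceilings, because events before loss are collected.

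**What one call could recover.** Assume 30% to 50% of lost subjects are reached, at equal risk. The relative gain runs from 0.02 × 0.30 = 0.6% to 0.05 × 0.50 = 2.5%.

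**The case against.** The strongest reply is the definition of the class. Telephone calls and certified mail have already failed, and Section 5.2.10 gives those efforts a safety purpose. Reachable non-attenders are classed elsewhere and stay in follow-up. Missing M6, M12 or M18 does not withdraw anyone in the Cohort 2 booster subset (Section 5.2.9). All of this stands and limits the affected group to people who are hard to find. A reader might infer that everyone who skips a visit is dropped, or that lost subjects are never phoned; these sections rule out both.

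Nor do lost subjects receive less than those who refuse, since a documented refusal ends contact too. The line in 5.2.12 follows contactability.

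The rule stops attempts by the site, not incoming reports. Subjects are repeatedly told to notify the site of SAEs and AESIs, and Section 10.3 requires reporting of related SAEs that occur after a subject has completed the study. Section 12.3.1 says losses will be identified and discussed in the report. These points stand, but none replaces an active contact.

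Finally, the footnote mainly fixes the dose from which the call is timed, 5.1.1 is a general statement, and a specific rule normally prevails. That is a fair reading. Still, the footnote presupposes that early-terminated subjects are phoned, and neither text points to the exception.

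**Conclusion.** The point holds as a modest one. Section 5.2.12 ends site attempts about five months before a call already in the schedule, and Section 5.1.1 and the footnotes do not carry that exception. Some late SAEs or AESIs may be missed, and the SAP denominator counts the subjects concerned as event-free for those months.

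The number affected is unknown. On assumed losses of 1% to 10% the effect on detection and on the zero-event bound is small, and the part a further call could recover is smaller. A reader might infer that late events are in fact lost, or that SAE rates are materially understated. The documents support neither, since they give no loss rate, no reach rate and no sign of higher risk in lost subjects. The absence of an IDMC does not strengthen the point: an internal team reviews safety during the study, and nothing ties that arrangement to this rule.

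**What to change.** In Protocol Section 5.2.12, confine the no-further-attempt sentence to subjects who withdrew consent and have a documented wish not to be contacted. For subjects lost to follow-up, require one attempt at the scheduled 6-month call, after the last primary dose or the booster as applicable, and record whether contact was made. Bring Section 5.1.1 and the schedule footnotes into line with that text.

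The Synopsis describes the Cohort 1 visits and calls as concluded, so the new wording can act only on Cohort 2 follow-up still to come, including the post-booster call. For all cohorts, add to the SAP a count by vaccine group of subjects with a completed 6-month contact, so that SAE and AESI rates can be read against actual follow-up.

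The cost is a wording change, one table row and a little site time on calls that may often fail.

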5.2.13 Follow-up and Reporting of Pregnancies

Pregnancy is an exclusion criterion for enrollment in this study, but a subject could potentially become pregnant during her participation. In case of pregnancy during the primary series and if at least 1 dose of the study vaccine(s) has been administered, the subject will not be discontinued from the study, but no further vaccination will be administered until after delivery (if applicable and still within the study vaccination window). However, the subject will be followed for safety assessment (and may be followed for immunogenicity assessment, if applicable).

All pregnancy cases should be reported if they occurred:

- Throughout the entire study period (for subjects in Cohort 1 and for subjects in Primary Series Cohort 2)
- From the first vaccination in Primary Series until the end of the 6-month follow-up after Primary Series or from the Booster Injection until the end of the 6-month follow-up after Booster Injection (for subject in Immunogenicity Persistence and Booster Phase Cohort 2).

To report the pregnancy case, the Investigator must fill out Pregnancy Reporting forms in the electronic data capture (EDC) system and inform the Sponsor within 1 month of identifying a pregnancy case.

If the EDC system is not available, the Investigator must fill out a paper Pregnancy Reporting Form (provided by the Sponsor at the start of the study) and inform the Sponsor within 1 month of identifying a pregnancy case.

Study staff must then maintain contact with the subject to obtain information about the outcome (ie, details about the delivery and the newborn, or about pregnancy termination) and must update the Pregnancy Reporting forms even after the end of the study. This information should be provided to the Sponsor within 1 month of delivery.

Pregnancy itself is not considered an AE, but any complications during pregnancy are to be considered as AEs, and in some cases could be considered SAEs. Spontaneous abortions, blighted ovum, fetal death, stillbirth, and congenital anomalies reported in the baby are always considered as SAEs, and the information should be provided to the Global Pharmacovigilance (GPV) Department regardless of when the SAE occurs (eg, even after the end of the study).

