5.2.5 Exclusion Criteria

An individual fulfilling *any* of the following criteria is to be excluded from study enrollment:

- 1) Subject is pregnant, or lactating, or of childbearing potential and not using an effective method of contraception or abstinence from at least 4 weeks prior to the 1st vaccination and 1 month after each vaccination. To be considered of non-childbearing potential, a female must be pre-menarche^b or post-menopausal for at least 1 year, or surgically sterile.
- 2) Participation at the time of study enrollment or, planned participation during the present study period in another clinical study investigating a vaccine, drug, medical device, or medical procedure.
- 3) Receipt of any vaccine in the 4 weeks (28 days) preceding the 1st study vaccination or planned receipt of any vaccine prior to V05 for pediatric subjects and adult subjects in Cohort 1, and prior to V04 for adult subjects in Cohort 2.
- 4) Previous vaccination against rabies (in pre- or post-exposure regimen) with either the study vaccines or another vaccine.
- 5) Bite by, or exposure to a potentially rabid animal in the previous 6 months with or without PEP.
- 6) Receipt of immune globulins, blood or blood-derived products in the past 3 months.

^a " \geq 1 year" means from the day of the 1st birthday onwards, with no upper age limit

^b Pre-menarche females will declare by themselves that they have not yet started menstruation. If a young female subject reaches menarche during the study, then she is to be considered as a woman of childbearing potential from that time forward.

- 7) Known or suspected congenital or acquired immunodeficiency; or receipt of immunosuppressive therapy, such as anti-cancer chemotherapy or radiation therapy, within the preceding 6 months; or long-term systemic corticosteroid therapy (prednisone or equivalent for more than 2 consecutive weeks within the past 3 months).
- 8) At high risk for rabies exposure during the study^a.
- 9) Known systemic hypersensitivity to any of the study/control vaccine components, or history of a life-threatening reaction to the vaccines used in the study or to a vaccine containing any of the same substances^b.
- 10) Self-reported thrombocytopenia, contraindicating IM vaccination.
- 11) Bleeding disorder, or receipt of anticoagulants in the 3 weeks preceding inclusion, contraindicating IM vaccination.

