5.2.7 Contraindications for Subsequent Vaccinations

5.2.7.1 Temporary Contraindications

Should a subject experience one of the conditions listed below, the Investigator will postpone further vaccination until the condition is resolved. Postponement must still be within the timeframe for vaccination indicated in the [Table of Study Procedures](#) (except for VAC2 in Cohort 2 which can be given after resolution of temporary contraindication(s) to permit the subject fully benefit from the rabies vaccination). If any dose is delayed, the subsequent doses should be delayed according to the original time interval.

- Moderate or severe acute illness/infection (according to Investigator judgment) on the day of vaccination or febrile illness (temperature $\geq 38.0^{\circ}\text{C}$).
- For Primary Series Cohort 2: unplanned administration of a vaccine other than the study vaccine between D0 and last primary vaccination (D07-VAC2). Since this is a PrEP study and the subjects will benefit from the rabies vaccination, the subject can receive the 2nd rabies primary dose at least 4 weeks after receipt of another vaccine (out of window) but will be excluded from the Per-Protocol Analysis Set (PPAS) – see [Section 12.2.4](#).
- For Immunogenicity Persistence and Booster Phase Cohort 2: administration of a vaccine other than the study vaccine 4 weeks prior to or planned administration within 4 weeks after booster vaccination, only if the delayed booster vaccination can still be maintained within the

allowed time window (M24-36 +14 days). If the allowed time window cannot be applied; please refer to [Section 5.2.7.2](#).

- Note: Vaccinations other than study vaccine consist of prohibited therapies within 28 days before and after each study vaccination ([Section 6.9](#)), their administration results in exclusion from PPAS and protocol deviation. The decision whether or not this would consist of a significant non-compliance with the protocol (condition for withdrawal from the study) depends on Investigator's judgment. There are no restrictions for receipt of other vaccines, including COVID-19 vaccination, in other study time frames: between V05 (Cohort 1) or V04 (Cohort 2) and 4 weeks before booster visit, or > 28 days after booster vaccination.

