5.2.7.2 Definitive Contraindications

Should a subject experience 1 of the conditions listed below, the Investigator will discontinue vaccination:

- Pregnancy, as indicated by a positive urine test.
- Anaphylactic or other significant allergic reaction to the previous dose of vaccine.
- Immunoglobulin, blood or blood-derived products received in the past 3 months or ongoing at the visit.
- Immunosuppressive therapy such as anti-cancer chemotherapy or radiation therapy in the past 6 months or ongoing at the visit, or long-term systemic corticosteroid therapy (for more than 2 consecutive weeks in the past 3 months before the visit).
- Human immunodeficiency virus (HIV) seropositivity.
- Thrombocytopenia, bleeding disorder or receipt of anticoagulants contraindicating IM vaccination.
- For Primary Series Cohort 1: administration of a vaccine other than the study vaccine between D0 and last primary vaccination (VAC3) or planned administration before V05.
- For Booster Phase Cohort 1: administration of a vaccine other than the study vaccine 4 weeks prior to or planned administration within 4 weeks after booster vaccination.
- For Immunogenicity Persistence and Booster Phase Cohort 2: administration of a vaccine other than the study vaccine 4 weeks prior to or planned administration within 4 weeks after booster vaccination, only if the temporary contraindication for the booster (see [Section 5.2.7.1](#)) could not be applied since it would not permit to keep visits schedule within the allowed window.
- An SAE related to the study vaccines following a vaccination.
- Any potential contact with rabies virus during the course of the study.
- Reporting of Guillain-Barré syndrome.

Subjects with a definitive contraindication will continue to be followed up for the study-defined safety and immunogenicity assessments, as applicable.

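### After a pregnancy in the primary series, Section 5.2.7.2 stops vaccination for good while Section 5.2.13 lets it resume, so the Cohort 2 booster has two rules; lactation has none.

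*Protocol*

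**What the plan says.** Protocol Section 5.2.7.2 opens with "Should a subject experience 1 of the conditions listed below, the Investigator will discontinue vaccination", and its first item is "Pregnancy, as indicated by a positive urine test". It has no clause on resuming. It does keep these women under observation: "Subjects with a definitive contraindication will continue to be followed up for the study-defined safety and immunogenicity assessments, as applicable".

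Protocol Section 5.2.13 sets a different rule for a narrower case. It begins "In case of pregnancy during the primary series and if at least 1 dose of the study vaccine(s) has been administered", keeps the woman in the study, and continues that "no further vaccination will be administered until after delivery (if applicable and still within the study vaccination window" allows. It adds that pregnancy itself is not an adverse event.

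Section 5.2.7.1, the list for which "the Investigator will postpone further vaccination until the condition is resolved", names neither pregnancy nor lactation.

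At entry, Section 5.2.5 excludes on both grounds: "Subject is pregnant, or lactating, or of childbearing potential and not using an effective method of contraception". The V08 procedures in Section 5.1.4.2 call for a urine pregnancy test, a medical history and a check against Section 5.2.7.

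Section 5.2.11, which classifies reasons for leaving the study early, puts a definitive contraindication that is not an adverse event under protocol deviation.

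**The concern.** Two sections give different instructions on further doses after the same event, and neither says which prevails. The person deciding at V08 can support either decision from the text. That decision determines whether a woman receives a booster of a vaccine that is not yet licensed and, for some women, whether she enters the booster analysis set.

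Section 5.2.13 also foresees vaccination after delivery. That is a period in which a woman may be lactating, and the protocol treats lactation as a bar at entry but does not mention it for any later dose.

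**Working it through.** **1. The two rules side by side**

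| | Section 5.2.7.2 | Section 5.2.13 |
|---|---|---|
| Trigger | Positive urine test, any later dose | Pregnancy during the primary series, after at least 1 dose |
| Vaccination | Discontinued | Withheld until after delivery |
| Resumption | None stated | Allowed if still in window |
| Follow-up | Continues | Continues |

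The rules agree on follow-up and on giving no dose during pregnancy. They differ only on doses after delivery.

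**2. Which doses can fall after delivery?**

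Assumptions not in the documents: conception to delivery takes 245 to 280 days; conception lies between D-14 and the day the pregnancy is found; one month is 365.25/12 = 30.4375 days.

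Delivery dates:
- Found at V02 (by D8): −14 + 245 = D231 to 8 + 280 = D288.
- Found at Cohort 1 V03 (by D31): D231 to 31 + 280 = D311.
- Cohort 2, found by the end of the 6-month follow-up (7 + 6 × 30.4375 + 14 = D203.6): D231 to 203.6 + 280 = D483.6.

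Dose windows:
- Cohort 1 VAC3, D25 to D31 (Protocol Section 12.2.3.1): closed 231 − 31 = 200 days before the earliest delivery.
- Cohort 2 VAC2, D7 +1 day (Tables of Study Procedures): closed 231 − 8 = 223 days before it.
- Cohort 1 booster, M12 to M12 +14 days: would open 365.25 − 311 ≈ 54 to 365.25 − 231 ≈ 134 days after delivery. Section 5.1.1 reports these boosters as given, and Section 5.1.5 dates the end of that phase August 2021.
- Cohort 2 booster, 24 × 30.4375 = D730.5 to 36 × 30.4375 + 14 ≈ D1,109.8. For a pregnancy found at V02 it opens 730.5 − 288 = 442.5 to 730.5 − 231 = 499.5 days after delivery. For one found by the 6-month follow-up it opens 730.5 − 483.6 = 246.9 to 499.5 days after.

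For the primary doses both sections lead to no dose. For the Cohort 2 booster they diverge.

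**3. What counts as the primary series?**

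SAP Section 4.3.4.1 and the SAE periods in SAP Section 5.1.2.2 run it through the 6-month follow-up. Section 5.2.13, in its reporting paragraph, speaks of a follow-up after the primary series, which suggests a shorter span. If it ends at V04 (35 + 3 = D38), the latest delivery is 38 + 280 = D318, and the booster opens 730.5 − 318 = 412.5 days later. The divergence remains, for fewer women.

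**4. Effect on FASB2**

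FASB2 requires a complete primary series and the booster (Protocol Section 12.2.1). A woman positive at V02 receives no VAC2 under either section, so she cannot enter FASB2, although her booster decision still differs. A woman who had both doses and became pregnant afterwards is in FASB2 under one section and out under the other.

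**5. Lactation**

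It appears in Section 5.2.5 but not in Sections 5.2.7.1, 5.2.7.2 or 5.2.13, nor in the V08 steps. For the Cohort 2 subset, Section 5.2.13 does not require pregnancies to be reported between the 6-month follow-up and the booster. A woman could conceive and deliver in that interval, attend V08 lactating with a negative test, and meet no stated rule.

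**6. Section 5.2.11**

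A pregnancy is a definitive contraindication (5.2.7.2) and not an adverse event (5.2.13), so Section 5.2.11 would class it as a protocol deviation reason for early termination. Section 5.2.13 keeps the woman in the study. Section 5.2.11 only classifies subjects who do leave, so this is a tension rather than a flat contradiction.

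**The case against.** The strongest reply is that Section 5.2.7.2 works as a visit-by-visit check. At V08 a woman who has delivered tests negative and passes. No urine test is scheduled between V02 and V08, so a woman who had both doses may never have produced a study test that triggers the section. This has force, and it makes the exclusion under Section 5.2.7.2 arguable rather than certain. It does not settle the matter. The heading says definitive, a separate list exists for pauses, and other items carry a look-back of 3 or 6 months where the pregnancy item carries none.

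Several stronger readings are tempting, and the documents do not support them:
- *A pregnancy first found at M24 meets both rules.* It does not. Section 5.2.13 is limited to pregnancy during the primary series, so Section 5.2.7.2 alone applies.
- *VAC2 in Cohort 2 could be given after delivery with no latest day.* The out-of-window exception in Section 5.2.7.1 covers temporary contraindications. No section makes pregnancy one, and Section 5.2.13 itself requires the dose to be in window.
- *Pregnant women are put at risk.* Neither rule allows a dose during pregnancy.
- *Sites will differ.* One site runs all of Cohort 2.
- *All 230 planned subset members are exposed to the conflict.* Only women with a pregnancy in the primary series or its follow-up are.

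It can also be said that entry exclusions need not all recur as later contraindications. That is true: the lactation point is an omission, not a contradiction. It needs an answer because the protocol itself foresees vaccination after delivery.

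**Conclusion.** The conflict is real and narrow. It bears on the Cohort 2 booster for a woman who was pregnant during the primary series or its 6-month follow-up and has since delivered. It changes FASB2 only if she completed both primary doses. The documents give no pregnancy rate, so the number cannot be derived; it is some part of the women among the 230 planned for the subset. The primary and key secondary analyses, their power and their error rate are not affected.

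The conclusion rests on Section 5.2.7.2 continuing to apply after delivery, which the text suggests but does not state. The timing rests on the assumed gestation lengths. With at least 247 days between delivery and the opening of the booster window, modest changes to those assumptions do not matter. The lactation gap stands independently of these points.

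**What to change.** Reconcile Sections 5.2.7.2, 5.2.11 and 5.2.13 so that one rule governs the booster after a pregnancy in the primary series. The reconciled text should say whether the primary series in Section 5.2.13 includes the 6-month follow-up, and whether the pregnancy item in Section 5.2.7.2 means a positive test at the visit or at any time since enrollment. State how lactation is handled at V08 and carry it into the V08 steps. Which clinical rule applies is for the clinical team to decide.

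For the report, add booster status to the pregnancy listing already foreseen in SAP Section 4.3.1.3.1, so that the number affected is known.

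The cost is protocol wording and a letter to the one Cohort 2 site. If the amendment is substantial, Section 5.4 requires IEC/IRB approval and submission to the regulatory authorities; it asks for IEC/IRB approval of administrative changes too. No visit, sample or analysis changes.
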